Retrospective audit: Pelvic radiographs from both sites obtained for the same time period in 2019 (June to September) will be assessed for image quality and to identify any recurrent issues (rotation, included anatomy, and image quality). Differences and similarities between the two retrospective cohorts will be assessed. An update on the retrospective audit will be provided to both sites as part of the prospective study training (see below).

Prospective data collection: All radiographers at the interventional site will undertake training on the different centring point, consisting of a video presentation and online Q&A session to embed the different technique. The training will be based on the literature, retrospective audit, and the findings of a recent unpublished evaluation [24] and article in press [1], which demonstrated high variability of centring points within pelvic radiographs and supported the proposal for a different centring point.

The control group will have a refresher update on pelvic positioning based on the retrospective audit. They will then continue with their usual practice and the technique used to position the patient (identified anatomical landmarks; field centring) will be documented on a case report form.

Sampling strategy

Patients presenting for pelvic radiography who fit the inclusion exclusion criteria will be sent a participant information sheet (PIS) with their appointment or given one in clinic and/or on arrival in radiology. Posters explaining the research will also be placed in each Department's waiting area.

A core group of study delivery radiographers, who have received GCP research awareness training will be responsible for obtaining informed written consent at both sites. Patients who agree to take part will sign a consent form agreeing to participation. The number of patients approached versus the number recruited will be recorded in a screening log.

Sample size

Based on unpublished pilot data, we would aim to reduce centring point variation with an effect size of 75%. This would require a total sample size, between the two study sites, of 314 (significance level 5%, power 80%) and would be achievable given the workload between the sites. Recruitment would be on a 1:1 basis.

Eligibility

Patients presenting for pelvic radiography who fit the inclusion exclusion criteria presenting to either of the clinical sites for pelvic radiography within the study period

Inclusion criteria

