All adult patients referred for a pelvic radiograph from outpatient (OP) clinics and general practitioners (GPs).

Exclusion criteria

Patients referred for one or both hip radiographs (XHIPB). Anyone with a hip prosthesis as the anatomical measures will not be valid. Immobile patients who may need additional adjustments to techniques. Patients <18 years old or pregnant. Those unable to read the participant information leaflet (PIS) or unable to provide informed written consent due to a lack of capacity (Mental Capacity Act).

Withdrawals/declining to participate

Participants may decline to participate or withdraw from the prospective study at any time without providing an explanation and without any detriment to their care. A decision to decline to consent or to withdraw will not affect the standard of care that the patient receives, as all patients will follow the diagnosis and management pathway appropriate to their clinical and radiological findings regardless of inclusion. Where patients decline to participate, no routinely collected information will be sought from NHS hospital systems about their attendance.

Study processes

Retrospective audit

The audit will be registered with each hospital site (MYH and WHTH). As the data is anonymised at source the study team will not have access to patient details thus individual consent from patients will not be sought.

The retrospective audit will be conducted for the time period of July to October 2019 to reflect the same period of the prospective study, and avoid variation in attendance numbers which may have been due to COVID-19

Prospective study:

This is a prospective interventional two arm study. One site will undertake training and then use the different technique for pelvic radiography centring (the interventional arm) and the other site will continue with usual practice. Both sites will receive feedback on the results of the retrospective audit prior to data collection via a short presentation.

Patients presenting for pelvic radiography who fit the inclusion exclusion criteria will be sent a participant information sheet (PIS) (Appendix 1) with their appointment or given one in clinic or on arrival in radiology. Posters explaining the research will also be placed in each Department's waiting area.

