Prospective data from both sites will include patient demographics (age, gender, height, and weight) and sagittal diameter at the centring point (Appendix 3). This will be recorded for each patient in the X-ray room to maintain dignity. The justification for imaging and the resultant radiograph, along with any repeats, will be collected by the research group and the resultant images will be scrutinised for axial, sagittal, and coronal rotation; image quality, and missing anatomy. This will be recorded in a password protected Excel workbook.

In the prospective cohort consented patients will undergo pelvic radiography based on the different technique or usual care, dependent upon which site they present to. The radiographer will record this, alongside the patient demographics detailed above, and justification for imaging, on a case report form (CRF – Appendix 3). The records will be anonymised and stored in a locked filing cabinet prior to analysis. The records sheet will be retained by the research team and anonymised data will be uploaded to the EDGE research management software to enable recruitment information to be collated by the NIHR portfolio and local CRN. Export of the data attributes from EDGE will be undertaken and the completely anonymised database shared with the research team for analysis. Anonymised images will be collected in DICOM format enabling analysis to be undertaken remotely. The radiation dose data will also be recorded.

Data management

Data security

The original versions of the screening logs, consent form, and CRFs will be stored in a locked filing cabinet within a locked research office at each study site. Only the research team will have access to this data. The electronic version of any data will password protected and stored on a secure drive only accessible to the direct research team. All patient identifiable information will be removed and transfer will be through encrypted devices or secure nhs.net email. All reports and dissemination of findings will only include anonymised data.

Quality control

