The research team will incorporate a rigorous programme of quality control. At regular intervals, study data will be exported from EDGE into an Excel spreadsheet and validated by a member of the research team with any data queries checked against source data. The main trial site (MYH) has an established monitoring audit programme for research studies with sponsored studies guaranteed to be appraised as part of this process, the same processes will be established at the other site (WHTH). Missing data will be recorded as an empty value.

Outcome measures

Statistical evaluation and data analysis

The data from the retrospective audit from both sites will be evaluated to determine the variability of axial, sagittal and coronal rotation; image quality, and included anatomy.

Prospective data from both sites will be analysed with descriptive and inferential statistics ICC's and Bland Altman plots (if the data is normally distributed). Data will be stratified according to Body Mass Index (BMI) in the following categories:

STOPPAGE protocol Version 1. 23.3.21 IRAS Project ID: 294098

- Underweight/Normal (BMI < 25)
- Overweight (BMI 26-30)
- Obese/morbidly obese (BMI >30)

Primary data analysis will determine the reliability of the centring point in the different technique versus usual care for sagittal, axial and coronal rotation; image quality, and included anatomy.

Secondary data analysis will compare results from within and between both sites to determine if the training and implementation of the different technique has any effect on the following:

- Obturator width left and right
- Axial pelvic rotation (degrees)
- Inter-acetabular line
- Pelvic outlet diameter
- Femoral head diameter left and right
- Inter-trochanter width
- Radiation dose
- Number of repeat radiographs
- Image quality as measured on the CRF form and from the exposure index
- Included anatomy from the iliac crests to the greater trochanters

For radiation dose data, and the number of repeats, the median and 75th percentiles will be compared.

The anonymised staff comments on the individual patient CRF's across both study arms will be descriptively analysed and a thematic analysis undertaken of any free text comments (see CRF Appendix 3).

Dose evaluation

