The data collected at both sites will include the radiation dose, measured as Dose Area Product (DAP). This will be compared to both local and national Diagnostic Reference Levels (DRL's) 2019 [34]. If any radiographs require repeating due to inadequate technical quality then these will be recorded along with the DAP. All repeat radiographs will be stored on PACS locally and transferred to the research team anonymously, no study images will be 'rejected'.

The radiographs will be undertaken with the use of Automatic Exposure Controls (AEC's) which feedback to the control panel and deliver the optimum radiation dose to the patient based on patient thickness and density (attenuation). Patient thickness will be calculated by subtracting the source object distance (SOD) from the source image distance (SID). Participant height and weight will also be recorded to allow evaluation of the effect of BMI on the subsequent radiographic technical quality.

The exposure Index (E.I.) will also be recorded for each patient. The E.I. is the measure of the amount of exposure received by the image receptor (IR). It is dependent on mAs, total detector area irradiated, and beam attenuation. The exposure index is indicative of the receptor dose, hence inherent signal to noise ratio (a measure of image quality)

Study Management

Patient and Public Involvement (PPI)

This proposal was developed with the advice and contribution of two Patient and Public Involvement (PPI) representatives from one of the study sites. The research idea was presented to the representatives and their views sought on the relevance of the research and appropriateness of the

research methods proposed. The PPI were consulted on, and approved all patient facing documents, and the group gave an opinion regarding privacy and dignity issues relating to obtaining patient size characteristics and the palpation of pelvic landmarks. Advice was incorporated and aided in a refined study proposal. PPI involvement will continue during study monitoring and when disseminating study findings. The PPI team will formally continue to the publishing of a lay summary of research findings.

Study Support

The CoRIPS grant is providing the funding. They will have no intellectual property (IP) rights to the data or outcomes arising from this study. Local CRN support will be sought help with recruitment and site file monitoring.

Dissemination

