Local dissemination will be led by the radiographers involved in the study delivery. It is also intended that these results will be presented at national and international conferences (UKIO and ECR). The radiographers will be supported in writing the abstract and presenting the research. The investigators will pursue publication of the results in relevant journals including Radiography and Clinical Orthopaedics. Open access will be preferred.

Use of social media and infographics (Twitter, LinkedIn and Facebook) will be used to publicise the research study and disseminate the results once the study has ended, the PPI group and participants will be encouraged to engage with these for feedback on the study.

Posters will be displayed at the participating NHS sites to feedback to patients and the radiography teams.

Ethical considerations

The key ethical consideration is identification of inadequate techniques in the retrospective audit and prospective study with respect to the pelvic radiographs.

To mitigate this and to provide quality assurance the radiographers at both sites will be provided with an overview of the main issues identified in the retrospective audit. All images will be assessed for quality throughout the study, providing opportunity for interventions if any variation from the protocol is identified.

No individual radiographer will be identified in the study.

Adverse Event Management

This study will be conducted in accordance with International Conference on Harmonisation Good Clinical Practice (ICH-GCP) principles and guidelines, the Declaration of Helsinki, Mid Yorkshire Hospitals Standard Operating Procedures (SOPs), relevant UK legislation and this protocol. ICH-GCP trained personnel will conduct the study.

ICH- GCP definitions of Adverse Events (AE) and Serious Adverse Events (SAE) will be used. Pelvic radiographs and the imaging protocols are used in everyday practice and their safety profile is well established. The different technique introduced at the interventional site has been robustly tested with an existing study looking at retrospective images. It is not envisaged that the different centring technique will impact on the safety of patients or radiographers.

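### ICC and Bland-Altman are the only specific methods named, but each patient is imaged with one technique, so they cannot estimate the primary between-technique difference in variability; no unpaired comparison of spread is specified.

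*Protocol*

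**What the plan says.** Under Statistical evaluation and data analysis the protocol says: "Prospective data from both sites will be analysed with descriptive and inferential statistics ICC's and Bland Altman plots (if the data is normally distributed". The same section adds: "Primary data analysis will determine the reliability of the centring point in the different technique versus usual care", for rotation in three planes, image quality and included anatomy. No other specific inferential method is named for these outcomes.

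The design is given under Study processes: "This is a prospective interventional two arm study", with one site per arm. Data collection confirms that "consented patients will undergo pelvic radiography based on the different technique or usual care, dependent upon which site they present to". On reading the images, it says that "the resultant images will be scrutinised for axial, sagittal, and coronal rotation; image quality, and missing anatomy"; it mentions no second reader and no repeat reading. The only repeat exposures are those under Dose evaluation: "If any radiographs require repeating due to inadequate technical quality then these will be recorded along with the DAP".

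The aim is about spread. The Synopsis hypothesis is that the new centring point lowers the variability of pelvic measurements, and the Sample size section says "we would aim to reduce centring point variation with an effect size of 75" per cent.

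**The concern.** An ICC divides variance between and within units that are measured more than once. A Bland-Altman plot shows differences between two measurements of the same unit. The primary comparison is between two techniques used on different patients at different hospitals, so neither statistic can be formed for it. The hypothesis concerns the dispersion of two independent groups, and neither named method compares that.

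At stake is whether the main result answers the main question. An analyst who follows the named methods will either find no pairs, or will compute an agreement statistic on something else (readers, or left against right) and report it as the reliability of the technique. The protocol fixes methods that do not match its own design, so this is more than detail left for a later analysis plan.

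**Working it through.** 1. **Search for pairs.** The possible sources of two measurements on one patient are:
   - Both techniques on one patient: none, because technique is fixed by site (Data collection).
   - Planned replicate exposure: none described.
   - Repeat radiographs: taken only after technical failure (Dose evaluation). They are a selected set of failures within one site, not replicates and not a cross-technique pair.
   - Second or repeat reading: none described.
   - Left and right obturator width and femoral head diameter (Statistical evaluation): pairs within a patient, but they describe symmetry under one technique.

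   Cross-technique pairs: 0 of 314.

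2. **The protocol's own figure.** The total of 314 (157 per site at 1:1, 5% significance, 80% power) might have shown which analysis was intended. It does not, because the scale of the 75% effect, the baseline and the test are not given.
   - Standardised mean difference 0.75, two-sided: 2 × (1.960 + 0.842)² / 0.75² = 27.9, so 28 per arm and 56 in total. Conversely, 157 per arm implies d = 2.802 × √(2/157) = 0.316.
   - Two-sided F test on variances: a variance ratio of 0.75 needs 764 in total, and an SD ratio of 0.75 needs 194. A variance ratio of 0.25 needs 38, and an SD ratio of 0.25 needs 12.
   - Two proportions can give 314, but only with an unstated baseline, such as 0.65 against 0.4875 (two-sided, continuity-corrected).

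3. **Is an unpaired comparison of spread feasible?** Assume normal, independent data with 157 per arm. The standard error of the log variance ratio is √(2/156 + 2/156) = 0.160. The ratio detectable with 80% power is exp(−2.802 × 0.160) = 0.64, an SD ratio of √0.64 = 0.80. The 95% CI for the SD ratio runs from the estimate divided by, to the estimate multiplied by, exp(1.96 × 0.160 / 2) = 1.17. The design can support this analysis, before any loss to clustering.

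4. **Would an ICC within each arm do instead?** Suppose images were read twice, and assume a reader-error variance of 1 and a usual-care between-patient variance of 9.
   - Usual care: ICC = 9/10 = 0.90.
   - New technique with 25% less between-patient variance: 6.75/7.75 = 0.87.
   - New technique with 75% less: 2.25/3.25 = 0.69.

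   The technique with less spread gets the lower ICC, so the statistic would point the wrong way.

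5. **Clustering by radiographer.** The protocol gives neither the number of radiographers nor how much their spread differs, so both are assumed. Simulations used about 160 patients per site, no true difference, and radiographer-specific SDs with the stated coefficient of variation (CV). The unadjusted Brown-Forsythe test at nominal 5% rejected as follows (ranges are separate simulation runs):

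| CV of radiographer SDs | 32 per site | 16 per site | 8 per site |
|---|---|---|---|
| 0.1 | 6% | 7% | 9% |
| 0.2 | not run | 11% | 18% |
| 0.3 | 11% | 17–19% | 28–30% |

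   Without clustering it rejected 4% to 5%.

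**The case against.** The strongest reply is that the sentence naming ICC and Bland-Altman covers all prospective data and also lists descriptive and inferential statistics, while the sentence defining the primary analysis names no method. SDs by site and an unpaired test are therefore allowed, and matching tests to endpoints is often left to an analysis plan. This stands in part. A reader might infer that the primary analysis, as written, can yield no estimate at all; the text does not go that far. It is the two named methods that cannot answer the question, and nothing suitable is named beside them.

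Second, ICC and Bland-Altman may be meant for reader agreement. That would be a valid use, but the protocol does not state it, and it would assess the reading rather than the centring technique.

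Third, the Primary research question concerns the new centring point across body habitus, and variability against usual practice is listed among the secondary questions. The statistical section nevertheless makes the comparison primary. Spread across body habitus, with one image per patient, is not what the named methods estimate either.

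Several stronger readings are tempting but not supported:
- That the plan ignores radiographers, or bars any adjustment for them. Training, CRF completion and staff comments all involve them. The statement "No individual radiographer will be identified in the study" is a confidentiality commitment and is compatible with an anonymous code. The CRF appendix is not shown, so the absence of a code cannot be asserted.
- That a particular inflated error rate applies here. The clustering inputs are assumptions.
- That the normality condition is wrong. The text does not say whether it refers to raw values or differences.

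**Conclusion.** The point holds. The only specific methods named for the prospective data cannot estimate or test the between-technique difference in variability, because no patient contributes a pair across techniques. This rests on the stated design and needs no numerical assumption. An unpaired comparison of spread is needed. With 157 independent, normally distributed observations per arm it would have 80% power for an SD ratio of about 0.80.

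The clustering part is secondary and conditional. With assumed CVs of 0.1 to 0.3 and 8 to 32 radiographers per site, an unadjusted Brown-Forsythe test rejects about 6% to 30% of the time under no difference. The true figure is unknown. No choice of statistic separates technique from site when each arm is a single hospital.

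**What to change.** Amend Statistical evaluation and data analysis as follows:
- Make the primary analysis an unpaired comparison of spread. For each continuous rotation measure, report the between-site ratio of SDs with a 95% CI.
- For included anatomy, and for image quality recorded as acceptable or not, report the difference in proportions with a 95% CI.
- Keep ICC and Bland-Altman only for repeat readings of the same images, if any are made, and say so.
- If an anonymous radiographer code is on the CRF or can be added, base both the interval and the test on a method that allows for clustering by radiographer, not on an unadjusted Brown-Forsythe test. A plain percentile bootstrap of radiographers is not enough with few of them: under the simulation assumptions its nominal 95% interval covered about 88% with 8 per site and 92% with 16. Choose a method with a small-sample correction. The code should be in place before recruitment, because it may not be recoverable later.
- State as a limit on the conclusion that technique and site are confounded.

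The cost is a wording change, at most one extra CRF field, and somewhat wider intervals.

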The different centring point being evaluated at the interventional site is based on features of the key anatomy being studied (the hips) and could be relevant regardless of patient body habitus, anatomical variation (pelvic tilt) and orientation (supine or standing). There is a clear gap in knowledge as to whether centring derived from different surface anatomy reference points result in the same image, radiation dose, and diagnostic quality and there is a need for greater standardisation in clinical practice and a robust underpinning evidence base.

The aim of this study is to provide evidence for a different centring point that has been developed from a previous image review study [1, 33] and determine its reliability and acceptability to radiographers. Providing evidence for optimum position is the first step to ensure radiography is evidence based and allows future development of an evidence base for other body parts. In addition, it provides a platform from which to consider changes to technique, such as the increasing requirement for weight-bearing images.

Principal aim of the study

To validate a different centring point for pelvic radiographs in a supine position.

Primary research question

What is the variability between the different pelvic centring point in a range of patient body habitus?

Secondary research questions

- Does the different centring point undertaken at the interventional site lower the number of X-ray repeats when compared to usual practice undertaken at the control site?
- What is the variability in pelvic radiographs (i.e. rotation and inclusion of anatomy) with the different method versus 'usual practice'?
- What is the average radiation dose for the different centring point compared to usual practice?
- What are the perceptions of radiographers in the ease of using the different centring point?

Methods

This study will test the different centring point for reliability and acceptability. Two NHS clinical sites in England will be used with one undertaking pelvis radiography according to the different technique (intervention site) and the other continuing with standard practice (control site).

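### The BMI strata are not exhaustive: a patient with a BMI from 25 to below 26 belongs to none of them

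*Protocol*

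**What the plan says.** In the protocol, the section on statistical evaluation and data analysis states: "Data will be stratified according to Body Mass Index (BMI) in the following categories". The three categories that follow are "Underweight/Normal (BMI < 25", "Overweight (BMI 26-30" and "Obese/morbidly obese (BMI >30". The section gives no rounding rule for BMI and no rule for a patient who fits none of the three.

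Four other places bear on the point:

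- **Primary research question:** "What is the variability between the different pelvic centring point in a range of patient body habitus".
- **Dose evaluation:** "Participant height and weight will also be recorded to allow evaluation of the effect of BMI on the subsequent radiographic technical quality". BMI is therefore calculated from two measurements.
- **Inclusion criteria:** "All adult patients referred for a pelvic radiograph from outpatient (OP) clinics and general practitioners (GPs". No inclusion or exclusion criterion refers to BMI.
- **Sample size:** a total "of 314 (significance level 5%, power 80"%), recruited 1:1 across the two sites.

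**The concern.** A set of strata should place every patient in exactly one category. Here the lowest category ends strictly below 25 and the next begins at 26, which leaves an interval one BMI unit wide with no category. It lies between the normal and overweight labels, where an unselected adult outpatient and GP population is likely to have a fair number of patients.

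What is at stake is the stratified analysis. BMI is the only body-size stratification that the analysis section states, and the primary research question asks about variability over a range of body habitus. If the categories are applied literally, the affected patients appear in no stratum and the stratum totals fall short of the number analysed. If they are not, someone must decide where these patients go after the data exist, with no rule written down. The outcomes of interest are spread and reliability, so who sits at the edge of a stratum can alter the result for that stratum.

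**Working it through.** **Step 1: coverage check.** The inputs are the three categories as printed: BMI < 25, 26 ≤ BMI ≤ 30, and BMI > 30. Count how many categories contain each value.

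| BMI | < 25 | 26 to 30 | > 30 | Categories |
|---|---|---|---|---|
| 24.9 | yes | no | no | 1 |
| 25.0 | no | no | no | 0 |
| 25.5 | no | no | no | 0 |
| 25.9 | no | no | no | 0 |
| 26 | no | yes | no | 1 |
| 30 | no | yes | no | 1 |
| 30.1 | no | no | yes | 1 |

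The gap is 25 ≤ BMI < 26. The boundary at 30 has neither gap nor overlap.

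**Step 2: does rounding close it?** No. With BMI rounded to whole numbers, the value 25 (true BMI 24.5 to below 25.5) fails the strict limit below 25 and lies under 26. The gap moves by half a unit but remains.

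**Step 3: size.** The protocol states no figure for this, so there is none to reproduce. It gives no BMI distribution either; I assume a normal distribution with mean m and SD s, and use the planned total of 314.

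- Share in the gap = Φ((26 − m)/s) − Φ((25 − m)/s)
- Patients in the gap = 314 × that share
- Share of those with BMI 25 to 30 = gap share ÷ [Φ((30 − m)/s) − Φ((25 − m)/s)]

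For m = 26 and s = 4.5: Φ(0) − Φ(−0.222) = 0.5000 − 0.4121 = 0.0879, and 314 × 0.0879 = 27.6. The 25 to 30 band holds 0.8130 − 0.4121 = 0.4009, so the gap is 0.0879 ÷ 0.4009 = 21.9% of it.

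For m = 29 and s = 6: Φ(−0.5) − Φ(−0.667) = 0.3085 − 0.2525 = 0.0560, and 314 × 0.0560 = 17.6. The band holds 0.5662 − 0.2525 = 0.3137, so the gap is 0.0560 ÷ 0.3137 = 17.9% of it.

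| Mean, SD | Share in gap | Patients of 314 | Share of BMI 25 to 30 | Patients if rounded to whole numbers |
|---|---|---|---|---|
| 26, 4.5 | 8.8% | 27.6 | 21.9% | 27.1 |
| 27, 5 | 7.6% | 23.9 | 20.0% | 23.1 |
| 28, 5.5 | 6.5% | 20.5 | 18.7% | 19.6 |
| 29, 6 | 5.6% | 17.6 | 17.9% | 16.7 |

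Other pairings of mean and SD within these limits stay inside 5.6% to 8.8%. A wider set of assumptions (mean 26 to 30, SD 4 to 6) gives about 16 to 31 patients, or 13% to 22% of those with BMI 25 to 30.

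**Step 4: after the correction.** With < 25, 25 to 30 and > 30 on unrounded BMI, every value falls in exactly one category and the gap holds no patients.

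**The case against.** The best case against the point accepts the gap and disputes its weight.

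- **Exclusion.** A reader might infer that these patients drop out of the study's analysis. The protocol does not say so. It says only that data will be stratified, and the affected patients stay in the unstratified comparisons of dose, repeats and pelvic measurements. This objection stands.
- **Link to the primary question.** A reader might also infer that the BMI strata carry the primary analysis. The sentence defining the primary data analysis does not mention BMI, and the primary objective in the synopsis mentions neither BMI nor body habitus. Sagittal diameter (patient thickness) is collected as a second measure of body size, and the gap does not touch it. This also stands. What remains is that the primary research question names body habitus and that BMI is the only body-size stratification in the analysis section, so the strata bear on that question.
- **Obvious intent.** A patient at 25.5 fails the limits of the lowest and highest categories, so only the overweight label is left, and 26 looks like a slip for 25. That is probably right and makes arbitrary assignment less likely. The printed rule still does not place the patient, so the text should be corrected.
- **No demonstrated effect on inference.** The same categories apply at both sites, and no effect on bias, type I error or power has been shown. This stands and limits the severity.

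**Conclusion.** The strata are wrong as written. The gap from 25 to below 26 is certain from the text and does not depend on how BMI is rounded. It is not detail left for a statistical analysis plan, because the protocol itself fixes the cut-points.

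The severity is minor. The consequence is confined to the BMI-stratified analysis, and the likely intent is easy to guess. The counts (about 18 to 28 of 314, roughly a fifth of those with BMI 25 to 30) are illustrative: they rest wholly on an assumed normal distribution with mean 26 to 29 and SD 4.5 to 6, and on the planned total being reached with height and weight recorded for everyone. The documents do not support a claim that patients are lost from the study or that the primary comparison is compromised.

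**What to change.** Before analysis, change the lower limit of the middle category from 26 to 25, so that the strata read < 25, 25 to 30 and > 30, and state that they apply to unrounded BMI calculated from recorded height and weight. This changes one number and adds a short clause. It does not affect recruitment, data collection or the unstratified comparisons.

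The cut at 30 need not move. An analysis on continuous BMI is an optional addition and is not needed to close the gap.
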